### 1.14.5 Lost to Follow-Up

A subject will be considered lost to follow-up if the following occurs:

- Subject misses 3 consecutive study visits (phone check-up and/or in-person visit),
- Subject cannot be reached by telephone following 2 consecutive missed visits (3 documented attempts by telephone made within ~2 weeks after the second missed visit), and
- Subject does not respond to the registered letter sent after the 3 attempted telephone contacts.

### 1.14.6 Withdrawal of Subjects from the Study

#### 1.14.6.1 Reasons for withdrawal

A subject should be withdrawn from the study and participation discontinued, if any of the following occurs:

- *Screen failure (before randomization):*
  - Subject has clinically-significant abnormal lab results at screening, unless approved by sponsor and PI
  - Subject has QTc>460 ms for male or >480 ms for female at screening, unless approved by the sponsor and PI
  - The investigator or sponsor is in the opinion that subject would not be appropriate for the study, for reasons including but not limited to, non-compliance during the run-in period, pre-existing condition or health risk.
- *Drop-out:*
  - Subject withdraws consent
- *Treatment interruption:*
  - Upon permanent treatment interruption, subject should be withdrawn after completion of a final follow-up visit, which should occur preferably within 1 month of treatment interruption (see section 1.14.3).
- *Unmasking:*
  - A subject's study treatment assignment becomes unmasked to subject, study team or the masked sponsor staff (except in the case of unintentional masking, in which case the sponsor and investigator shall decide).
- *Lack of compliance:*
  - Subject is unable or has not complied with intake of the study drug, except when approved by sponsor or in case of medication shortage
  - Subject misses a follow-up visit window and is judged by investigator as unable to comply with the visit schedule, except when approved by sponsor
  - Subject becomes pregnant
  - Subject has undergone eye examination(s) or imaging, outside the scope of this study, which in the opinion of the investigator could affect the progression of the disease or the procedures or data collected in this study, except when approved by sponsor (see 1.12.35.1)
  - Subject has received concomitant treatment, which in the opinion of the investigator may affect the progression of the disease or the procedures or data collected in this study, except when approved by sponsor.
- *Medical reasons:*

- The investigator and sponsor both agree that it is not in the best interest of the subject to continue participation, for reasons including but not limited to, non-compliance or health risk.
- Subject develops a medical condition that requires concomitant therapy with a prohibited medication (See section [1.11.3](#)).
- Subject develops a life-threatening adverse reaction, or a serious adverse reaction that places them at immediate risk.
- Subject permanently interrupts treatment according to one of the reasons of section [1.14.4](#).
- Subject experiences a QTc interval > 500 ms or an increase of QTc greater than 60 ms, based on average QTc value of duplicate ECG, except if approved by sponsor.
- Subject is dead.

- *Lost to follow-up:*

- Subject is lost to follow-up, after every reasonable effort has been made by the study team to contact the subject and determine the reason for discontinuation/withdrawal. All efforts and measures must be documented.

#### **1.14.6.2 How to withdraw a subject and discontinue study participation**

If a subject is to be withdrawn from the study and participation discontinued:

- subject is asked to stop taking the study drug,
- an early termination visit should be scheduled within approximately 1 month following the administration of the last dose of study drug (see section [1.14.3](#)), and
- all remaining study drug should be returned to the site, including all empty bottles, partially empty bottles, or unopened bottles,
- investigator should make reasonable efforts to ascertain the reason(s) for withdrawal, while fully respecting the subject's rights.
- All findings should be fully documented.

All study drug returned by the subject should not be used or administered to another subject, except upon written request by the sponsor.

#### **1.14.7 No Replacement of Subjects**

Withdrawn subjects will not be replaced by new subjects, except upon written request by the sponsor. Therefore, it is important to only enroll participants who are likely to adhere to the schedule of the study visits, to the self-administered treatment regimen, and to the procedures performed during the study visits.

#### **1.14.8 Data Collection**

All data collected up to the day the subject was withdrawn will be used.

### **1.15 STATISTICAL METHODS**

A statistical analysis plan (SAP) will be generated before data analysis and will describe all planned statistical analyses. The **SAP should supersede the below statistical sections of this protocol in case of discrepancies between such sections and the SAP.**

#### **1.15.1 Sample Size Determination and Power Calculation**

Sample size calculation was based on review of all available literature data on the progression of GA. With 300 subjects enrolled in the study and assuming that 80% of subjects are evaluable for the primary outcome measure, the study has an 80% power to detect, after 24 months of treatment, a 33% slowing in

GA growth rate with a 2-tailed significance of 0.05, assuming a conservative standard deviation of 1.5 sqmm/year and an average GA growth rate of 1.8 sqmm/year in the control group.

As part of the exploratory measure, and assuming that 35% of enrolled subjects have a fellow eye with active or history of CNV, the study has an 80% power to detect, after 24 months, a 75% reduction in incidental progression to CNV in the study eye with a 1-tailed significance of 0.2 (Fisher's exact test).

### 1.15.2 Interim Analysis

Interim efficacy analyses, if any, will be performed according to the SMC charter and the statistical analysis plan. Safety data will be reviewed periodically by the SMC as described in the section below.

### 1.15.3 Safety Monitoring Committee (SMC); Interim Data Analyses

An independent SMC will be established to monitor the study data on an ongoing basis and to ensure the continued well-being of subjects enrolled in this study. The committee shall meet periodically, but no less than once a year, to review safety data. SMC may organize ad hoc meetings if required, or may change the frequency of meetings based on findings, enrollment or other factors.

The SMC may make recommendations about the study design or execution. A SMC charter shall supersede this protocol in case of conflict. The SMC shall be composed of at least 3 members, with no less than 2 voting members. To ensure proper masking of the study team, investigators, study team, sponsor staff who interact with the investigators and/or subjects, cannot be members of the SMC. The SMC should consist of at least 1 medical expert in the field of ophthalmology and at least 1 statistics expert. SMC members may be amended from time to time.

SAEs will be communicated on an ongoing basis to the SMC. The SMC may have access to unmasked data upon request and review tabulated summaries and any additional data the SMC may request during the study. The sponsor, representative and monitors should review masked data from the sites and notify the SMC of any issues relevant to subjects' health. In no event should current or former SMC members communicate unmasked data, results, analyses or randomization code to anyone outside of the SMC.

Content of summaries, SMC role and responsibilities and general procedures, including communications and recommendations on the study conduct, will be defined and documented in the SMC charter. Initial charter and SMC members shall be organized within approximately 6 months from the enrollment of the first subject in this study.

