Scientific Rationale	
GA is an advanced form of AMD, characterized by well-demarcated atrophic lesions of the RPE and outer retinal layers. Symptoms of GA include uncorrectable central vision loss and other disturbances, along with the inability to see fine details, read, write, recognize faces, or drive. GA is currently untreatable, progressive, and leads to legal blindness.
 
Retinaldehyde-derived dimerization byproducts (RDDB) are molecules that form non-enzymatically in the retina as byproducts of the visual cycle. RDDBs include molecules such as “A2E” and other vitamin A dimers, as well as their downstream degradation or combination byproducts. RDDBs form and gradually accumulate with age in the retina. These molecules are toxic to the retina and have been shown to cause, for example, chronic oxidative stress, inflammation, dysregulation of the complement, angiogenesis, and poisoning of the lysosomes, which are thought to contribute to the pathophysiology of AMD. Strategies to prevent RDDB formation have been explored as possible treatments of GA. To date, these strategies have relied on “modulating the visual cycle,” by decreasing the vitamin A supply or its flow in the retina. Such approaches lead to adverse reactions such as night blindness, dark adaptation delays and chromatopsia, and might lead to long-term retinal toxicity.
 
ALK-001 is a chemically-modified vitamin A whereby 3 hydrogen atoms have been selectively replaced by heavy hydrogen (also known as “deuterium”). Because deuterium and hydrogen are similar, ALK-001 preserves normal biological functions of vitamin A. Daily intake of ALK-001 leads to rapid replacement of the majority of vitamin A with a modified vitamin A that forms RDDB several folds slower, without affecting the visual cycle. As such, ALK-001 is not a visual cycle modulator. ALK-001 is a “clean tool” that can be used in clinical studies to measure the extent to which slowing RDDB formation retards the progression of GA and the incidence of CNV.

Study Duration	Approximately 3 years, including 8 months of enrollment, 24 months of treatment period, and 4 months of data analysis.
Study Center(s)	Multicenter.
Primary Objective	To assess the effects of ALK-001 on the growth rate of GA lesions after 24 months of treatment in patients with GA secondary to AMD.

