## **1.5 BACKGROUND INFORMATION**

This document is the protocol for a multi-center phase 2/3 clinical trial to evaluate the effects of ALK-001, an investigational new drug (IND), on the progression of geographic atrophy (GA) secondary to age-related macular degeneration (AMD).

Subjects enrolled in the study will be instructed to take one capsule per day containing ALK-001 or placebo for a period of 24 months. Up to approximately n = 300 subjects will be enrolled in the study. Subjects will be randomized 2:1 ALK-001:Placebo without stratification. At the end of the 24-month treatment period, subjects may be offered to enroll into an optional open-label, long-term extension, to evaluate the long-term effects of ALK-001.

Study visits will be scheduled to take place every ~6 months, with optional visits every ~3 months, essentially similar to US practices standard of care follow-up for GA patients. Every ~6 months, subjects will perform imaging and visual function tests, and undergo safety testing (including evaluation of adverse events, clinical lab tests, physical and/or ocular evaluation and management). At the optional 3-month visits, subjects will perform clinical lab tests.

To cover a clinically-representative population of patients with GA, only one (1) eye will be required to have GA (“study eye”), as GA lesion size will be measured to evaluate the primary endpoint. The fellow eye will present with at least one of the following features (a) GA, (b) intermediate AMD, characterized by a large macular drusen, or (c) historical or active choroidal neovascularization (CNV).

The area of GA will be measured using fundus autofluorescence (FAF) imaging, and will be characterized by well-demarcated dark lesions, and confirmed on optical coherence tomography (OCT) imaging. Subjects who present with or develop CNV during the study will be managed according to each site standard of care.

This study will be conducted according to US and international standards of Good Clinical Practice (GCP), applicable government regulations and institutional research policies and procedures. The sponsor of the study, Alkeus Pharmaceuticals, is dedicated to the subjects’ rights and wellbeing and, prior to and during the course of the study, will ensure proper communication with and training of the investigators and study team, as well as monitoring of the study. An independent Safety Monitoring Committee (SMC) will monitor safety data throughout the trial.

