## **1.7 STUDY DESIGN AND RATIONALE**

### **1.7.1 Overview of Trial Design**

This is a randomized, double-masked, parallel-group, multicenter study evaluating the safety and efficacy of ALK-001 in subjects with GA secondary to AMD. Approximately 300 subjects who match all eligibility criteria will be randomized to receive either ALK-001 (n = 200) at 14 mg/day or placebo (n = 100) for 24 months in a 2:1 drug:placebo ratio. After 24 months of treatment, an optional open label extension is planned to determine the lowest chronic dose that can maintain approximately 80% of deuterated vitamin A in plasma.

[figure not shown]
The expected total duration of the study from first patient first visit to last patient last visit, excluding the optional open label extension is 2 years and 9 months, which includes a total of up to 2 years of treatment with the study drug and 9 months of enrollment. Subjects, investigators and study team, and sponsor staff who may be in contact with investigators or subjects, will be masked for the duration of the study.

Safety and tolerability will be assessed by monitoring AEs, clinical laboratory tests, vital signs, ECG and physical examinations. The primary endpoint for assessment of efficacy is the growth rate of GA lesions

measured on FAF imaging and confirmed by OCT, between baseline and 24 months of treatment. Secondary efficacy endpoints include effects of ALK-001 on visual and ocular function and anatomy, as measured by questionnaires, BCVA, reading speed, and OCT. Exploratory outcomes measure include microperimetry and assessment of complement in the blood.

Protocol waivers or planned deviations may be allowed upon approval by sponsor and IRB when necessary. In certain cases, FDA review may be required, in which case such planned deviations or protocol waivers may be implemented only after receiving confirmation by sponsor that the FDA review period has been completed. Protocol waivers or deviations intended to eliminate an apparent immediate hazard to human subjects may be implemented immediately, provided that sponsor and IRB are subsequently notified, as required.

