#### *1.7.2.7 Safety Evaluations*

Based upon vitamin A's known safety and tolerability profile, possible AEs of interest have been identified and will be monitored during this study (see section [1.5.8.1](#)). Safety data will be acquired by: 12-lead ECG, physical exam, ocular exams, retinal photographs, clinical laboratory tests, bioanalytical tests (vitamin A), BCVA.

To make sure that any potential for hypervitaminosis A is detected, *symptoms* such as headaches, nausea, dry lips, dry skin, *signs* such as papilledema (optic disc swelling), and clinically meaningful abnormalities

in clinical laboratories will be explored (see section 1.16.1.6). In addition, levels of retinol, retinoic acid, and retinyl esters will be measured periodically. In order to avoid study unmasking, such data will be reviewed by the SMC. See section below on pharmacokinetic evaluations.

Vitamin A-related adverse reactions are usually reversible upon discontinuation of the vitamin.

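### The protocol lets the Safety Monitoring Committee be set up as late as about six months after the first randomisation, and until then no body is charged with group-level unmasked safety review

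*Protocol*

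**What the plan says.** The timing rule is the last sentence of Protocol 1.15.3 (version 1.1, on which the SAP is based): "Initial charter and SMC members shall be organized within approximately 6 months from the enrollment of the first subject in this study". Under section 1.9.1 a subject is enrolled only after randomisation, and section 1.9.4.1 has study drug dispensed usually on the same day. The clock therefore starts when the first subject goes on randomised treatment.

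Other parts of the protocol assume that the committee is already there:

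- Section 1.5: "An independent Safety Monitoring Committee (SMC) will monitor safety data throughout the trial".
- Section 1.7.1 names the SMC as the body that reviews unmasked safety data.
- Section 1.7.2.7, on plasma retinol, retinoic acid and retinyl esters: "In order to avoid study unmasking, such data will be reviewed by the SMC".
- Section 1.15.3 sends SAEs to the SMC continuously, and tells the sponsor and monitors to review masked data and alert the SMC to health issues.

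The same section sets a minimum of one SMC meeting a year and makes the charter prevail over the protocol where they conflict.

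**The concern.** A committee without members or charter cannot receive SAEs, look at data by arm or ask for an ad hoc review. The staff who run the trial day to day (sponsor personnel, sites, monitors) are masked under section 1.9.7.1. Some other roles hold the treatment code, such as the unmasked statistician, the unmasked monitor and the drug supply designee, but the protocol gives none of them a safety-review task. If SAEs clustered in the active arm early on, nobody would have the job of noticing.

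This matters because the population is new to the drug. Section 1.5.9 gives safety in patients aged 60 and over as an aim of the study, and section 1.5.7.2 reports that subjects in the earlier studies were aged 13 to 62. Planned enrolment is also short, so a window of about six months covers a large part of it.

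**Working it through.** **Inputs**

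- Latest set-up of the SMC: about 6 months after the first randomisation (Protocol 1.15.3 and 1.9.1).
- Enrolment period in the synopsis (1.1): "Approximately 3 years, including 8 months of enrollment, 24 months of treatment period, and 4 months of data analysis". Check: 8 + 24 + 4 = 36 months, or 3 years, as stated.
- Enrolment period in section 1.7.1: "which includes a total of up to 2 years of treatment with the study drug and 9 months of enrollment". Check: 24 + 9 = 33 months, or 2 years 9 months, as stated.
- Size and allocation (1.5): "Up to approximately n = 300 subjects will be enrolled in the study"; "Subjects will be randomized 2:1 ALK-001:Placebo without stratification". Two-thirds of those randomised are on ALK-001.
- Accrual shape: not given. Two shapes are assumed: a constant rate, and a rate that rises linearly from zero.

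**Formulas**, with T the enrolment period in months

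- Share randomised by month 6: 6/T at a constant rate; (6/T)² at a linearly rising rate.
- Subjects: 300 × share. On ALK-001: two-thirds of these.
- Patient-months by month 6, with no early stopping: 300 × 6²/(2T) at a constant rate; 300 × 6³/(3T²) at a rising rate. Two-thirds are on ALK-001.

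| Accrual | T | Share | Randomised | On ALK-001 | ALK-001 patient-months |
|---|---|---|---|---|---|
| Constant | 8 | 6/8 = 75% | 225 | 150 | 675 × 2/3 = 450 |
| Constant | 9 | 6/9 = 67% | 200 | about 133 | 600 × 2/3 = 400 |
| Rising | 8 | (6/8)² = 56% | about 169 | about 113 | 337.5 × 2/3 = 225 |
| Rising | 9 | (6/9)² = 44% | about 133 | about 89 | 266.7 × 2/3 = about 178 |

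More than half of planned enrolment falls in the window in three of the four cases. At a constant rate the share drops to half only when enrolment takes 12 months (6/12). A slower start than either assumed shape gives less: a rate rising with the square of time gives (6/8)³ = 42% or (6/9)³ = 30%.

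**Effect of the change.** With the SMC in place before the first randomisation, the number treated before it exists is 0 in every case.

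**Meeting frequency.** The only minimum is yearly. A committee formed on day one could still hold its first data review at month 12, after 8 or 9 months of enrolment have ended. Early appointment alone therefore does not secure a review during enrolment.

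**The case against.** The strongest reply is that subjects are not left unwatched. Sites collect adverse events at every contact (1.16.1.1), the PI reviews every laboratory report (1.12.29), liver and ECG rules can stop treatment (1.14.4), and the PI oversees subjects' wellbeing (1.16.2). SAE forms reach the sponsor within 24 hours (1.16.3.1), and the sponsor may unmask an individual for a health risk at any time (1.9.7.3). All of this stands, and it protects individuals.

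It also rules out two stronger readings. A reader might infer that detection of hypervitaminosis A rests with the SMC alone. It does not: section 1.7.2.7 relies first on symptoms, signs such as papilledema and routine laboratory results, all of which sites follow. A reader might also infer that no one sees vitamin A levels before the SMC exists. Section 1.9.7.2 has the bioanalytical laboratory or a designated unmasked person review the PK data, and lets the sponsor and investigators see them in de-identified form. Section 1.7.2.8 adds that a level above normal may not mean toxicity when there are no clinical signs.

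Few retinoid results would exist in the window anyway. The Month 3 visit is optional (1.12.13), the first required post-baseline laboratory visit is Month 6 (SAP 7.3), and plasma is frozen and shipped on request (1.12.30). Section 1.5.8.1 considers vitamin A effects unlikely in roughly the first six months of treatment. The retinoid part of the gap is thus the weaker part. SAEs can occur from the first dose, and that part remains.

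An argument that interim efficacy looks could precede the charter also fails. Protocol 1.15.2 makes such looks conditional, and SAP 9.0 states that none was planned or performed.

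Finally, six months is an approximate upper limit, and SAP 3.1 reports enrolment delays and 200 randomised in all. The planned-size figure of 225 therefore exceeds the whole trial as run, and the actual share may have been lower.

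**Conclusion.** The point holds as a conflict in the plan and a gap in group-level oversight. The allowance in 1.15.3 cannot be squared with SMC monitoring for the whole trial, continuous SAE communication to the SMC, or SMC review of unmasked safety and retinoid data. Individual safeguards operate throughout, but until the SMC exists no body has a duty to review safety by arm.

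The size is about 133 to 225 of 300 planned subjects (44% to 75%), of whom about 89 to 150 would be on ALK-001. This rests on the full six months being used, on the stated 8 or 9 months of enrolment, and on the two assumed accrual shapes. The top of the range needs a constant rate from the first day. It describes what the plan permits. The documents do not say when the SMC was formed and give no enrolment dates, so they do not support an inference that it was in fact late or that any safety signal was missed.

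**What to change.** Replace the six-month allowance in Protocol 1.15.3 with a requirement that SMC members are appointed and the charter is signed before the first subject is randomised. SAEs then have an unmasked recipient from the start. Have the charter set the first data review during enrolment, since the yearly minimum does not ensure this. State one enrolment period in 1.1 and 1.7.1, which now differ (8 and 9 months).

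The cost is earlier administrative set-up of a committee that is already required, and possibly one earlier meeting. Sample size, endpoints and visits do not change.

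SAP 3.1 shows that randomisation is complete, so the rule can no longer be applied in this trial. What remains is to report in the clinical study report the date on which the SMC was constituted, the date of its first data review, and the number of subjects randomised by each.
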